^bCentral American other than Mexican

Ascertainment and Enrollment: Interviews. Eligible Latina survivors and caregivers will be recruited from our four sites or referred by a collaborating hospital or clinic. Contacts at each site will help identify eligible Latina survivors and will mail a study flyer inviting them and a primary caregiver to be involved in an in-depth interview. We will also use in-person recruitment to talk with survivors and caregivers at the four sites (e.g., at the time of patient navigation). If a survivor and/or caregiver is interested, a team member will follow up with further information about the study to determine eligibility and obtain consent from both individuals in the dyad.

Ascertainment, Enrollment and Retention: RCT. With over 2 years of enrollment into the RCT, we anticipate a total of 750 Latina survivor-caregiver dyads identified at the four

sites with a minimum of 300 eligible dyads. We will establish procedures to identify eligible women by having the Project Director/Project Manager (PD/PM) at each site develop an eligibility checklist for their use. The PD at GUMC will coordinate this process across sites to ensure consistency. The PD/PM will check in weekly with the PD at GUMC to provide names of women who provided permission for the team to contact them. We will recruit caregivers through Latina survivors, a strategy that has been very successful at Nueva Vida. We will enroll 125 dyads. We have retained over 80% of Latina survivors in prior work.²⁵ We thus expect to retain 100 survivor-caregiver dyads at 6-months. We will discuss strategies to promote retention through teleconferences and annual meetings. We will customize strategies to each site.

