Randomization. After the baseline, we will randomize participants to PCI or UC via computer by the method of permuted blocks with blocks of size four. We will stratify randomization by location (DC, NY, CA). The GUMC PD will help guide each site PD/PM on accessing/using the web-based randomization database. Randomization is expected to balance key demographic factors such as age, time since diagnosis and survivors' stage of disease between the PCI and UC arms. We will carefully examine these factors in analyses and control any variables as appropriate.

RCT Implementation. Following randomization, survivor-caregiver dyads will begin either the PCI or proceed with UC. PCI sessions will be held at one of the four community partner sites and led by the trained bilingual and bi-cultural interventionists. Interventionists will work with the PD in DC to track intervention delivery process measures and participant attendance. We will use rolling recruitment and begin new groups as we enroll participants. Groups will consist of approximately 10 survivor-caregiver dyads each (n=20 in each PCI wave; n=10 in each PI wave). Groups will be closed such that newly enrolled participants will wait to begin a group until ~10 new dyads are identified.

Post-intervention and 6-month Follow-Up Interviews. Follow-up interviews assess QOL, secondary outcomes, proposed mediating variables (communication self-efficacy, social support, distress), cultural, contextual and dyadic factors (Table 4). We also will assess intervention process. Follow-up interviews will be 25 minutes and administered by telephone and conducted by the bilingual RA using internet-based data entry screens through the PROMIS Assessment Center. Participants will receive \$10 for each completed interview.

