Data Analyses. Aim 1. *To evaluate the impact of the PCI intervention on Latina survivors' and caregivers' QOL.* **H₁:** Survivors and caregivers in PCI will report higher QOL compared to those assigned to UC. Aim 1 analyses will be performed separately for the Latina survivors and carriers. With 50 Latina survivors (and caregivers) per arm we will have 84% power to detect a clinically significant difference in QOL of 6 points (0.6 SD on PROMIS QOL measures) at a significance level of 0.05. Changes of PROMIS of 5 points or more are clinically significant.⁶⁰ We will use a mixed effects model to compare the two arms with respect to QOL immediately post intervention and at 6-months, adjusting for statistically significant (at the 0.10 level) predictors of QOL identified in bivariate analyses. In addition to this intent-to-treat analysis, we will perform a "per protocol" comparison of intervention completers vs. non-completers (defined as attending fewer than five sessions). We will use a mixed effects model to compare these groups on QOL immediately post intervention and at 6-months, controlling for potential confounders associated with both intervention completion and QOL in bivariate analyses. As we expect the sample of Latina survivors and their caregivers in the present study to be representative of the over 8,000 individuals who seek services or information from the community organizations involved in the study, our findings should generalize to thousands of Latina women in the Washington DC, New York City and San Jose, CA areas. For the survivors we will also explore whether geographic region (DC, NY or CA), nationality (U.S. born vs. immigrant) or region of origin (e.g., Central America, South American) modifies the effect of the intervention on QOL. We will also explore whether caregiver gender impacts the effect of the intervention on QOL.

Aim 2. *To identify mediators of the PCI intervention on QOL.* **H₂:** Consistent with our experience and theoretical models, changes in QOL will be due to improved communication self-efficacy, improved social support and decreased distress among PCI participants vs. UC participants. Aim 2 analyses will be performed separately for the Latina survivors and caregivers. We will use the product of coefficients method to assess

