mediation effects at 6-months.¹¹⁹ We will use linear regression models to estimate the coefficients relating each mediating variable (self-efficacy, social support, and distress) to QOL at 6-months, and also the coefficients relating the intervention to each mediating variable. We will calculate the mediated effects as the products of corresponding coefficients and we will construct 95% confidence intervals according to the methods described by MacKinnon et al.¹¹⁹ With 50 subjects per arm we will have 80% power to detect mediation effects of moderate size (with coefficient parameters of 0.39 or more) for each mediator.¹¹⁹

Aim 3. To evaluate the impact of the PCI intervention on Latina survivors' satisfaction with their cancer care. **H₃:** Survivors in PCI will report greater satisfaction with their cancer care compared to UC participants. With 50 Latina survivors per arm we will have 96% power to detect a clinically significant difference in satisfaction with care of 8 points (0.75 SD given estimated SD of 12)¹²⁰ at a significance level of 0.05. We will use a mixed effects model to compare the two arms with respect to satisfaction with care immediately post intervention and at 6-months, adjusting for statistically significant (at the 0.10 level) predictors of satisfaction with care identified in bivariate analyses. We will again explore whether the effect of the intervention on satisfaction with care is different for sub-groups of participants (e.g., whether the impact of PCI on satisfaction with care differs by geographic region (e.g., NY,CA) or region of origin (e.g., Central America, South American)).

Exploratory Aim: To explore the impact of the PCI intervention on Latina survivors' adherence to guideline-concurrent care and surveillance. Given the exploratory nature of this aim no formal power calculation was performed. We will use logistic regression models to compare the two arms with respect to the binary outcomes of adherence to guideline-concurrent care (hormonal therapy; chemotherapy) and surveillance (mammogram within 12 months), controlling for the statistically significant (at the 0.05 level) covariates identified in bivariate analyses. We will also perform "per protocol" analyses of completers vs. non-completers similar to those described in Aim 1.

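### PCI is delivered in closed groups of about 10 dyads, but the Aim 1 and Aim 3 power figures and mixed model make no stated allowance for correlation within a session group

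*Combined protocol and SAP*

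**What the plan says.** Delivery in the PCI arm is by closed group (C.2, RCT Implementation): "Groups will be closed such that newly enrolled participants will wait to begin a group until ~10 new dyads are identified". "PCI sessions will be held at one of the four community partner sites". Under C.1, Patient-Caregiver Intervention, each wave has its own eight topics drawn from a longer list, and the groups meet eight times over four months. Under C.1, Usual Care (UC), the trial forms no groups in the comparator arm, although UC participants may use existing community support groups.

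The Aim 1 power statement (C.2, Data Analyses) is "With 50 Latina survivors (and caregivers) per arm we will have 84% power to detect a clinically significant difference in QOL of 6 points", equated there to 0.6 SD at a 0.05 level. The analysis is: "We will use a mixed effects model to compare the two arms with respect to QOL immediately post intervention and at 6-months". Survivors and caregivers are analysed separately.

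Aim 3 states "With 50 Latina survivors per arm we will have 96% power" for a difference in "satisfaction with care of 8 points (0.75 SD given estimated SD of 12", with the same type of model.

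On numbers, the enrolment section says "We will enroll 125 dyads" and "We thus expect to retain 100 survivor-caregiver dyads at 6-months".

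Two other places come near the issue. Appendix C would bring participants' ratings of interventionists into the analysis where judged appropriate, and item 7 of Replication of Research Findings promises a written analysis plan. Neither commits to a session-group term.

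**The concern.** People in the same PCI group share leaders, topics and peers for four months, so their outcomes may be correlated. UC participants have no corresponding trial group. The design is therefore partially nested: clustered in one arm only. Analysing survivors and caregivers separately removes the correlation within a dyad but leaves the correlation within a group.

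Two things are at stake. If groups differ in how much they help and the model has no group term, the standard error of the arm difference is too small and the nominal 5% test rejects too often when the average effect is zero. (If PCI affects no one, there is no inflation.) Second, a test that does account for groups has less unadjusted power than stated.

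The plan does not rule a group term out. Its mixed model covers two follow-up times, so it can be read as having a participant effect only, or as having a group effect too. The two readings give different standard errors.

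**Working it through.** **1. Reproduce the stated powers.** Two-sided two-sample t-test, alpha 0.05, 50 independent people per arm:

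- Aim 1, d = 6/10 = 0.6: 84.4% (stated 84%). A one-sided test gives 90.9%, so the plan's figure is two-sided.
- Aim 3, d = 0.75: 96.0% (stated 96%).
- Aim 3 from its own inputs, d = 8/12 = 0.667: 91.0%. For 0.75 SD to hold, the difference would have to be 0.75 × 12 = 9 points, or the SD 8/0.75 = 10.7.

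Both stated figures therefore assume independence.

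**2. Number of groups.** 125 enrolled dyads / 2 is about 62 in PCI; at about 10 per group that is about 6 groups. With 50 analysed, the average group size is m = 50/6 = 8.33.

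**3. Formulas**, in SD units, clustering in PCI only, equal total variance in the two arms:

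- Design effect: DE = 1 + (m − 1) × ICC
- Variance of the difference: (DE + 1)/50
- Large-sample power: Φ(d/SE − 1.96)
- Small-sample power: noncentral t, with Satterthwaite df combining 5 df (6 groups) for PCI and 49 for UC
- Type I error without a group term: 2 × [1 − Φ(1.96/√((DE + 1)/2))]

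Example at ICC 0.05: DE = 1 + 7.33 × 0.05 = 1.367; SE = √(2.367/50) = 0.2176; large-sample power = Φ(0.6/0.2176 − 1.96) = 78.8%; Satterthwaite df = 14.2, power 72.8%; type I error = 2 × [1 − Φ(1.96/1.088)] = 7.2%.

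**4. Results, 6 groups.** The ICC values are assumptions.

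| | ICC 0.01 | 0.02 | 0.05 | 0.10 |
|---|---|---|---|---|
| Satterthwaite df | 17.1 | 16.3 | 14.2 | 12.0 |
| Aim 1 power, Satterthwaite | 79.3% | 77.7% | 72.8% | 65.5% |
| Aim 1 power, large-sample | 83.8% | 82.5% | 78.8% | 72.8% |
| Aim 3 power (0.667 SD), Satterthwaite | 87.0% | 85.6% | 81.4% | 74.5% |
| Aim 3 power (0.667 SD), large-sample | 90.6% | 89.6% | 86.5% | 81.4% |
| Type I error, no group term | 5.4% | 5.9% | 7.2% | 9.4% |

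At ICC 0 the Satterthwaite figure for Aim 1 is 81.0%, so 84.4 − 81.0 = 3.4 points are the cost of having few groups rather than of correlation. On the large-sample basis, the no-clustering reference is 85.1%.

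**5. Sensitivity to the number of groups (Aim 1, Satterthwaite, same ICC order).** Five groups of 10: 77.8 / 75.6 / 69.5 / 60.4%. Eight smaller groups: 81.0 / 79.9 / 76.7 / 71.4%, with type I error without a group term of 5.3 / 5.6 / 6.5 / 8.1%.

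**6. Possible offsets (Aim 1, 6 groups, Satterthwaite).**

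| | ICC 0.01 | 0.02 | 0.05 | 0.10 |
|---|---|---|---|---|
| Covariates correlating 0.5 with QOL (assumed) | 88.9% | 87.1% | 81.7% | 72.9% |
| All 62 per arm contribute (upper bound) | 86.8% | 85.1% | 79.7% | 71.2% |
| Both | 94.0% | 92.5% | 87.1% | 77.7% |

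The covariate row multiplies the individual variance by 1 − 0.5² = 0.75 and leaves the group variance unchanged. At ICC 0.05 the large-sample figures for the two single offsets are 87.2% and 85.3%.

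**7. Behaviour of the group-variance estimate.** Simulation, 20,000 runs, groups of 9, 9, 8, 8, 8 and 8, one time point, no covariates, moment estimate. The estimate was zero or negative in 53 / 48 / 36 / 24% of trials across the four ICC values. Type I error was 5.1 to 5.2% with the variance left unconstrained, 3.9 to 4.5% if the term is dropped at zero, and 3.2 to 4.2% if it is truncated at zero with group-based df.

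**The case against.** The size rests on an ICC that the documents do not give. At 0.01 to 0.02 the large-sample loss is small (85.1% to 83.8% or 82.5%) and the type I error is 5.4% to 5.9%. The plan also works to limit differences between groups through joint training, a manual, checklists and fidelity review, although topic choice by wave works the other way. Part of the Satterthwaite loss is present even at ICC 0. Covariates and post-intervention data from dyads lost later could restore 84%. The number of groups is inferred, and smaller groups would soften the effect. The document is a funding-stage plan that promises a fuller protocol and analysis plan, so an unnamed random effect is incomplete rather than wrong.

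Most of this stands as a limit on size. None of it supplies the missing term. Gains in power do not correct a standard error that leaves out group variance, and the ICC will not be known before the analysis is chosen. The promised analysis plan is where the term belongs. It is also fair to say that the Aim 3 slip (8/12 is not 0.75) has nothing to do with clustering. It is included here only because the Aim 3 power has to be restated anyway.

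**Conclusion.** The concern holds. The stated 84% and 96% are independent-sample figures for a trial with one arm treated in groups, and no group term is specified for either aim. With 6 groups and an assumed ICC of 0.01 to 0.10, unadjusted Aim 1 power is 79.3% down to 65.5% (Satterthwaite) or 83.8% down to 72.8% (large-sample). Type I error without a group term is 5.4% up to 9.4%, provided group effects vary around a zero average. Under Satterthwaite df, either offset alone keeps Aim 1 power above 84% at ICC 0.01 to 0.02 but not at 0.05 to 0.10; both together do so at 0.05. Aim 3's 96% disagrees with its own 8 points and SD 12 whatever the ICC.

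This should be fixed: the term bears on the validity of the primary test, although its size is uncertain.

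**What to change.** For Aims 1 and 3, specify a partially nested mixed model with:

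- a random effect for the assigned PCI session group;
- UC participants treated as singletons, stated as an assumption;
- Satterthwaite or Kenward-Roger degrees of freedom.

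State in advance what happens when the group variance is estimated at zero or on the boundary, since with about 6 groups this will be common. Leaving the variance unconstrained is the better default on the simulation above; the other two rules are conservative, so what matters most is that one rule is fixed beforehand.

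Record each PCI participant's assigned group and analyse by it regardless of attendance.

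Restate Aim 1 power as a range over assumed ICC, leading with 6 groups: for example 78% (large-sample 83%) at ICC 0.02 and 73% (large-sample 79%) at 0.05. Show any gain from covariates separately, with its assumed correlation. Reconcile 8 points, SD 12 and 0.75 SD in Aim 3, then restate its power in the same way.

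The cost is analysis-plan wording and one group identifier per PCI participant; attendance and topics by group are already tracked. Intervals will be slightly wider and the stated unadjusted power less favourable. Neither the design nor the sample size changes.

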Conceptual Model. In addition to the empirical evidence of the key role of culture in health and psychosocial outcomes among Latina survivors and their family members,^{3,6,11,12} our proposed work is guided by two conceptual models. First, our work is influenced by the Contextual Model of Health-Related QOL.¹² This model specifies individual (e.g., disease characteristics) cultural (*familismo*, *personalismo*, social support, acculturation) and contextual influences (dyadic relationships, communication with physicians, satisfaction with care) as important determinants of QOL. The dyadic component of our model is derived from Berg and Upchurch,⁶² dyadic communication, perceived stress and communication reciprocally influence outcomes for both the patient and their partner or caregiver (Figure 2). Our proposed work is also in direct response to identified needs of Latina survivors, observations by a community organization that provides direct service and support to Latina survivors and recent calls in the cancer and caregiving literatures to involve family and incorporate cultural beliefs and values into interventions for cancer survivors and their caregivers.^{34,40}

Figure 2. Dyadic Contextual Model^{12,62}

Second, our intervention strategy is informed by Social Cognitive Theory.¹³ A key construct in Social Cognitive Theory is self-efficacy, or one's confidence in his or her ability to engage in specific behaviors. The intervention is designed to increase self-efficacy in communication between a survivor and her caregiver. The intervention

Table 4. Study Measures	Base-line	T1	T2
Background Factors			
Sociodemographics	X		
Medical History	X	X	X
Cultural Factors			
Breast Cancer Stigma	X	X	X
Religious Coping, Familismo	X	X	X
Acculturation	X	X	X
Medical-Contextual Factors			
Communication with Providers	X	X	X
Medical Mistrust	X	X	X
Mediating Variables			
Communication Self-efficacy	X	X	X
Social Support	X	X	X
Distress	X	X	X
Outcome Measure			
QOL (Using PROMIS)	X	X	X
Secondary Outcomes			
Communication (Provider)	X	X	X
Communication (Caregiver)	X	X	X
Satisfaction with Care	X	X	X
Adherence to Guideline-Concurrent Care	X	X	X
Dyadic Factors			
Dyadic Support	X	X	X
Dyadic Perspective	X	X	X
Social Constraints	X	X	X
Process Variables			
Intervention Satisfaction		X	X
Fidelity Measures		X	X
T1 = Immediately Post Intervention; T2 = 6-Months Post Intervention Completion			

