Interventionist Training. Our team has experience conducting interventionist training for psychosocial interventions with breast cancer patients⁶⁵ and specifically Latina breast cancer patients.^{16,18} Building on these skills, investigators will conduct a 2-day in-person training for the PCI interventionists. Training will involve a study overview and in-depth discussion of the intervention manual, topics for each session, therapeutic approaches and talking points to use during each session. Interventionist training will occur in person (DC and CA interventionists will travel to New York). We will have refresher interventionist training at our annual meetings to prevent drift.⁹³ We will also review intervention fidelity logs during weekly team teleconferences. Study investigators and consultants have trained interventionists from diverse backgrounds.^{16,18,66,76}

Implementation. Baseline Interview. After study enrollment and consent, we will call survivor and caregiver participants to schedule separate 30-minute baseline telephone interviews. If we have not received signed consent documents at that time, we will describe the study again and answer questions. If the participant agrees, we will obtain verbal consent to conduct the interview. Participants will not be randomized until after baseline completion by each member of the dyad. Interviews will be conducted by a trained research assistant

at GUMC using internet-based secure data entry screens through the PROMIS Assessment Center. The Assessment Center provides support services to investigator-initiated surveys and use of PROMIS domains^{85,86} delivered through computerized-adaptive testing. Guided by our conceptual model¹² (see Figure 2) we will assess background factors, cultural factors, medical-contextual factors, mediating variables, QOL outcomes, secondary outcomes and dyadic factors (see Table 4; Appendix D). We have experience with similar interviews. We will minimize interviewer bias with: 1) intensive training (e.g., mock interviews, standardized Q&A), 2) on-going interview monitoring by the PD, and 3) interview completion before randomization. Participants will receive a \$10 gift card.

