Avoidance of Bias: Study Limitations and Strengths. The proposed study has the following limitations: 1) Representation of only three geographic regions (New York, CA and Washington DC); this concern is mitigated by the diversity of the Latino populations at these sites. 2) Issues of mixed gender caregiver groups. We will explore caregiver gender as a covariate in our analyses. 3) Self-report of follow-up medical care. We will use established and validated measures from national surveys. 4) Use of incentives to enhance session attendance. We opted to include modest incentives to indicate our appreciation of participant's involvement in this research endeavor. Strengths include: 1) Test of an innovative, culturally-relevant intervention, 2) Inclusion of diverse and predominantly immigrant and monolingual Latino sample, 3) Involvement of a multi-disciplinary team through strong community-academic partnerships, 4) Use of PROMIS to measure QOL, 5) Attention to the reduction of bias through a) on-site interventionist training, b) different personnel to conduct intervention delivery and outcome assessment, c) efforts to blind outcome assessors to study assignment, d) use of strategies to promote intervention fidelity (see Appendix C), and e) prior and on-going engagement of patients, caregivers and key stakeholders in the development of the study questions, outcomes and implementation.

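### Aims 1 and 3 choose covariates by a p<0.10 screen on the trial's own outcome, so the baseline score and location are not guaranteed a place in the model

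*Combined protocol and SAP*

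**What the plan says.** C.2 Data Analyses, Aim 1, fits a mixed effects model to QOL at the two follow-ups, separately for survivors and caregivers, "adjusting for statistically significant (at the 0.10 level) predictors of QOL identified in bivariate analyses". Aim 3 uses the same 0.10 screen for satisfaction with care. The Exploratory Aim uses a 0.05 screen.

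The baseline score will be available for everyone (C.2 Baseline Interview): "Participants will not be randomized until after baseline completion by each member of the dyad". Location is the only stratification factor (C.2 Randomization: "We will stratify randomization by location (DC, NY, CA"), yet in Aim 1 it appears only as an exploratory effect modifier.

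Two other sentences touch covariates without fixing any. After mentioning age, time since diagnosis and stage, C.2 Randomization says "We will carefully examine these factors in analyses and control any variables as appropriate". The limitations paragraph adds "We will explore caregiver gender as a covariate in our analyses".

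Table 4 and the follow-up section show that the hypothesized mediators are measured again after randomization: "Follow-up interviews assess QOL, secondary outcomes, proposed mediating variables (communication self-efficacy, social support, distress", with "T1 = Immediately Post Intervention; T2 = 6-Months Post Intervention Completion".

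C.1 names QOL by PROMIS as the primary outcome and lists several PROMIS scores. Neither C.1 nor Aim 1 says which score, or which follow-up contrast, decides the hypothesis. The replication section promises a full protocol and a written analysis plan later.

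**The concern.** The rule lets the trial's outcome data decide the model. The two covariates with the clearest claim to inclusion, the baseline value of the same score and the stratification factor, are in only if they reach p<0.10. A mixed model could carry the baseline score as a response, but Aim 1 names only the two follow-ups. Because the candidate list is not written down, a reader cannot tell in advance what the model will contain, and nothing expressly keeps out variables measured after randomization, which the intervention may itself have changed. At stake are some precision and a primary model that can be checked against the plan.

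**Working it through.** **The plan's own figure.** Inputs from Aim 1: 50 per arm, 6 points = 0.6 SD (so SD 10), alpha 0.05, sidedness not stated. Noncentrality = 0.6 × √(50/2) = 3.0. A two-sided t-test with 98 df gives 84.4% (normal approximation 85.1%; one-sided about 91%). The stated 84% is therefore right for one unadjusted two-sided comparison of one score, at one time, in one population.

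**With the baseline score fixed.** Residual SD = 10√(1−r²); noncentrality = 3.0/√(1−r²) for 6 points. The correlation r is assumed. The 5-point column is included because Aim 1 calls changes of 5 points or more clinically significant.

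| r | Residual SD | Noncentrality (6 points) | Power, 6 points | Power, 5 points |
|---|---|---|---|---|
| 0 (unadjusted) | 10.00 | 3.00 | 84.4% | 69.7% |
| 0.3 | 9.54 | 3.14 | 87.6% | 73.7% |
| 0.5 | 8.66 | 3.46 | 92.9% | 81.6% |
| 0.7 | 7.14 | 4.20 | 98.6% | 93.4% |

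**What the screen would select at n=100.** A baseline score passes p<0.10 about 92% of the time at r=0.3 and over 99.9% at r=0.5. Location passes 22%, 45% or 72% of the time if it explains 1%, 3% or 6% of the variance. Location is the one more likely to be dropped.

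**Screen against fixed adjustment.** Simulation, 3,000 runs per setting: n=100, blocks of four in three locations, true effect 0.6 SD, no location effect, ten further candidates of which three are real predictors with joint R² as shown. Entries are power (%) for fixed baseline plus location / screen with baseline as a candidate.

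| r | R²=0 | R²=0.1 | R²=0.2 | R²=0.3 |
|---|---|---|---|---|
| 0.3 | 88.0 / 86.3 | 87.8 / 87.0 | 86.7 / 88.4 | 86.8 / 92.4 |
| 0.5 | 92.5 / 91.6 | 92.9 / 92.0 | 92.3 / 93.2 | 92.5 / 95.2 |
| 0.7 | 98.6 / 98.5 | 98.6 / 98.3 | 98.2 / 98.2 | 98.4 / 98.6 |

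With noise candidates only, fixing gains 88.0 − 86.3 = 1.7, 92.5 − 91.6 = 0.9 and 98.6 − 98.5 = 0.1 points. At most the screen gains 92.4 − 86.8 = 5.6 points, when there are strong unnamed predictors. If the three real predictors were correctly named in advance and also fixed, fixed adjustment ranged from 0.2 points below the screen to 1.5 above.

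**Type I error and bias.** At r=0.5 and R²=0.2, null rejection was 5.2% fixed and 5.3–5.6% screened. In a second simulation with 20 noise candidates, it was 4.6–4.9% fixed and 4.9% screened. There the screened estimate of a 0.6 SD effect averaged 0.575–0.582, against 0.599–0.601 fixed, an attenuation of 3–4%.

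**Less natural readings of the rule.**
- Baseline never a candidate, all others noise: screened power is 82.7%, 83.1% and 82.5% at r=0.3, 0.5 and 0.7, a loss of 5.3, 9.4 and 16.1 points.
- Follow-up mediators enter the Aim 1 model: borrowing Aim 2's figure ("mediation effects of moderate size (with coefficient parameters of 0.39 or more) for each mediator") for both paths, each mediator removes 0.39 × 0.39 = 0.152 SD, about 1.5 points. The 6-point effect is then estimated as about 4.5, 3.0 and 1.4 points with one, two and three mediators. At r=0.5, power is 79%, 56% and 23%, against 92–93% without them.

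**Unnamed score.** The C.1 list yields 9 to 11 scores, depending on how the social items are counted. If each were tested at 0.05 at one time in one population, the chance of at least one false positive would be 24–34% (assumed correlations 0.6–0.4).

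**The case against.** The strongest reply is that the screen costs almost nothing as it would normally be run. QOL at baseline is in Table 4, nothing in Aim 1 bars it as a candidate, and at r=0.5 or more it is practically certain to be selected. That stands: it is why the realistic gain is at most about 2 points, and why the screen sometimes wins. No separate cost of omitting location has been shown, since the main simulation had no location effect.

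A reader might infer more, and the documents do not support it:
- *That the screen inflates type I error.* The simulations show no material inflation.
- *That 5–16 points of power are lost.* This needs the baseline score never to be considered and every other candidate to be noise.
- *That Aim 1 will adjust away its own effect.* Table 4 lists mediators under their own heading and Aim 2 models them separately. Adjusting for them in Aim 1 is not excluded, but it is not the natural reading. The 0.39 is a detectable size, not an expected one.
- *That the false-positive risk is 24–34%.* The plan nowhere says it will test every listed score at 0.05; it speaks of QOL in the singular.
- *That a single primary time point is required.* One mixed-model contrast averaged over both follow-ups would be equally legitimate.

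The plan also defers detail. A final protocol is promised within 12 months, its submission is scheduled for Year 1 Q4, and data analysis starts in Year 2 Q4. That is after recruitment opens in Year 1 Q3, but about a year before analysis. The score and contrast may be settled there. For covariates, however, the present text states a definite rule, and that rule is what should change.

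**Conclusion.** The concern holds as a gap in prespecification with a free remedy, not as an error that threatens the trial. The 84% is correct as an unadjusted figure. Guaranteed baseline adjustment supports about 88%, 93% or 99% at assumed r=0.3, 0.5 or 0.7. The advantage over a screen that includes the baseline score is at most about 2 points with noise candidates, and it can reverse when real predictors are left off the prespecified list. Larger losses depend on readings that the plan leaves open but does not state. All figures assume independent participants and 50 per arm.

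The unnamed PROMIS score and contrast is a real but secondary omission. Whether the Aim 1 hypothesis needs success in both survivors and caregivers is a trade-off for the team, and this point does not prescribe an answer. For reference, power at alpha 0.025 in one population is 76.4% (88.1% at r=0.5). Holm across two populations treated as independent then gives:
- both: 0.844² − (0.844 − 0.764)² = 71%
- a given one: 0.764 + 0.080 × 0.764 = 83%
- at least one: 1 − 0.236² = 94%

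At r=0.5 these are 86%, 92% and 99%.

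**What to change.** In Aims 1 and 3, replace the screen with covariates kept whatever their p-values:
- the baseline value of the same score, as a covariate or as a constrained baseline response in the mixed model;
- location (DC, NY, CA);
- at most a short list of further baseline variables named before outcome data are seen. Strong predictors belong here, because this is where the screen would otherwise have the advantage.

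State that no measure taken after randomization enters these models.

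As a secondary clarification, name the PROMIS score and the contrast (one follow-up, or the average of both) that decide the Aim 1 hypothesis, with the other scores secondary.

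The cost is a few sentences and minor programming. No participants, interviews or items are added, since the baseline score and location are already collected.
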